### 9.1.1 Adverse (Drug) Reaction

All noxious and unintended responses to a medicinal product related to any dose should be considered an adverse drug reaction. “Responses” to a medicinal product mean that a causal relationship between a medicinal product and an adverse event is at least a reasonable possibility, i.e., the relationship cannot be ruled out.

### 9.1.2 Unexpected Adverse Drug Reaction

An Unexpected Adverse Drug Reaction is defined as an adverse reaction, the nature or severity of which is not consistent with the applicable product information.

The reference safety information for ASN100 is included in the current version of the Investigator’s Brochure. The reference safety information will be reviewed yearly and the periodicity of the review will be harmonized with the reporting period of the Development Safety Update Report.

### 9.1.3 Assessment of Adverse Events by the Investigator

The Investigator will assess the severity (intensity) of each adverse event as mild, moderate, or severe, and will also categorize each adverse event as to its potential relationship to study drug using the categories of yes or no.

#### Assessment of Severity:

Mild – An event that is easily tolerated and generally not interfering with normal daily activities.

Moderate – An event that is sufficiently discomforting to interfere with normal daily activities.

Severe – An event that is incapacitating with inability to work or perform normal daily activities.

#### Causality Assessment:

The relationship of an adverse event to the administration of the study drug is to be assessed according to the following definitions:

No (unrelated, not related, no relation) – The time course between the administration of study drug and the occurrence or worsening of the adverse event rules out a causal relationship and another cause (concomitant drugs, therapies, complications, etc.) is suspected.

Yes (related) – The time course between the administration of study drug and the occurrence or worsening of the adverse event is consistent with a causal relationship and no other cause (concomitant drugs, therapies, complications, etc.) can be identified.

The definition implies a reasonable possibility of a causal relationship between the event and the study drug. This means that there are facts (evidence) or arguments to suggest a causal relationship.

The following factors should also be considered:

- The temporal sequence from study drug administration:
  - The event should occur after the study drug is given. The length of time from study drug exposure to event should be evaluated in the clinical context of the event;
- Underlying, concomitant, intercurrent diseases:
  - Each report should be evaluated in the context of the natural history and course of the disease being treated and any other disease the subject may have;
- Concomitant drugs:
  - The other drugs the subject is taking or the treatment the subject receives should be examined to determine whether any of them might be recognized to cause the event in question;
- Known response pattern for this class of study drug:
  - Clinical and/or preclinical data may indicate whether a particular response is likely to be a class effect;
- Exposure to physical and/or mental stresses:
  - The exposure to stress might induce adverse changes in the recipient and provide a logical and better explanation for the event; and
- The pharmacology and PK of the study drug:
  - The known pharmacologic properties (absorption, distribution, metabolism, and excretion) of the study drug should be considered.

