### **9.3 Serious Adverse Event Reporting – Procedures for Investigators**

#### **Initial Reports**

Serious adverse events related to a study-specific procedure that occur between the Screening Visit and the Randomization Visit, and all SAEs occurring from the time of randomization until the Day 90 Safety Visit, must be reported to Medpace Clinical Safety within 24 hours of the knowledge of the occurrence (this refers to any adverse event that meets any of the aforementioned serious criteria). All SAEs that the Investigator considers related to study drug occurring after the Day 90 Safety Visit must be reported to the Sponsor.

To report the SAE, complete the SAE form electronically in the electronic data capture (EDC) system for the study. When the form is completed, Medpace Safety personnel will be notified electronically and will retrieve the form.

If the event meets serious criteria and it is not possible to access the EDC system, send an email to Medpace Safety at [[contact]](mailto:[contact]) or call the Medpace SAE hotline (phone number listed below), and fax the completed paper SAE form to Medpace (fax number listed below) within 24 hours of awareness. When the EDC system becomes available, the SAE information must be entered within 24 hours of the system becoming available.

Safety Contact Information: Medpace Clinical Safety

Medpace SAE hotline – USA:

[contact], Dial 3 or [contact], Dial 3

[contact] or [contact]

Email: [[contact]](mailto:[contact])

Medpace SAE hotline – Europe:

[contact]

[contact]

Email: [[contact]](mailto:[contact])

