7.3.3. Other Missing Data

Other missing values will not be imputed and only observed values will be used for reporting of descriptive statistics unless otherwise stated.

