7.13.1. Adverse Events

Verbatim descriptions of Adverse Events (AEs) will be coded using Version 19.1 of MedDRA. Summary tables will be provided for all Treatment-Emergent Adverse Events (TEAEs). A TEAE is defined as an AE with a start date and time on or after the initiation of study drug administration. If the time of an AE is missing, it is considered treatment emergent if it starts on the same date as the initiation of study drug administration. All AEs (including non-TEAEs), Serious AEs (SAEs), and AEs leading to study drug discontinuation will be provided in listings by treatment group, subject ID, verbatim term, MedDRA system organ class (SOC) and preferred term (PT), start and end date, seriousness flag, severity, relationship to study drug, and action taken with study drug.

An overall summary of AEs will include the number and percentage of subjects in each treatment group who experienced at least one AE/TEAE in the following categories: any AE, any TEAE, any drug-related TEAE, any severe TEAE, any SAE, any drug-related SAE, any SAE leading to death, any TEAE leading to discontinuation of study drug, and any SAE leading to study drug discontinuation. Subjects with multiple events will be counted only once within each category. Severity grade and relationship will be counted using the maximum severity and the strongest relationship respectively for a subject with multiple TEAEs.

The number and percentage of subjects reporting a TEAE in each treatment group will be tabulated by SOC and PT; by SOC, PT, and severity; and by SOC, PT, and relationship (unrelated or related to study drug). For all analyses of TEAEs, if the same AE (based on PT) is reported for the same subject more than once, the AE is counted only once for that PT and at the highest severity and strongest relationship to study drug.

The number and percentage of subjects reporting a SAE and reporting a TEAE leading to discontinuation of study drug in each treatment group will be summarized by SOC and PT.

Listings will be provided for SAEs and AEs leading to drug discontinuation. In addition, all AEs will be listed.

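### The two causality definitions in Protocol 9.1.3 leave an adverse event with plausible timing and another possible cause in neither category of a forced yes/no scale

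*Protocol*

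**What the plan says.** Protocol 9.1.3 asks the investigator to "categorize each adverse event as to its potential relationship to study drug using the categories of yes or no". The Causality Assessment text then defines the two answers by the time course between dosing and event:

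- 'No' applies when the time course "rules out a causal relationship and another cause (concomitant drugs, therapies, complications, etc.) is suspected".
- 'Yes' applies when the time course "is consistent with a causal relationship and no other cause (concomitant drugs, therapies, complications, etc.) can be identified".

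A sentence after the definitions says that they imply a reasonable possibility of a causal link. Six factors to consider follow, among them underlying disease and concomitant drugs.

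Protocol 9.1.1 sets a different standard for an adverse drug reaction: a causal relationship that "is at least a reasonable possibility, i.e., the relationship cannot be ruled out".

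SAP 7.13.1 uses the recorded answer. Its overall summary has rows for "any drug-related TEAE, any severe TEAE, any SAE, any drug-related SAE", among others, and TEAEs are also tabulated by system organ class and preferred term, split into unrelated and related. Its only rule on relationship is to take the strongest one when a subject has repeated events.

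Protocol 9.3 uses the answer as well: "All SAEs that the Investigator considers related to study drug occurring after the Day 90 Safety Visit must be reported to the Sponsor".

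**The concern.** The two definitions are not complements. Plausible timing fails the first condition of 'No', and another identifiable cause fails the second condition of 'Yes'. An investigator with such an event must still tick one box and has no text that says which.

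This is unlikely to be a rare case. Subjects are ventilated and in intensive care, Protocol 1.3 permits concomitant antibiotics throughout, and Protocol 4.2 does not exclude a history of sepsis. A fever soon after infusion in such a subject has plausible timing and an obvious rival explanation.

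Safety and tolerability are part of the primary objective, and Protocol 5.3 describes this as the first study in this population. If about 70 sites each settle the question in their own way, the drug-related rows have no single meaning. After Day 90 the same judgement decides whether the protocol requires an SAE to be reported to the Sponsor.

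**Working it through.** The plan gives no figure on this point, so the check is a truth table of the two definitions in Protocol 9.1.3, followed by a test of whether any other text fills the gaps.

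**Step 1. Apply the definitions.** There are two conditions (timing, other cause), each with two states, so 2 × 2 = 4 combinations.

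| Timing | Another cause | Meets 'Yes' | Meets 'No' | Result |
|---|---|---|---|---|
| Consistent | Absent | Yes | No | Related |
| Consistent | Present | No | No | Neither |
| Ruled out | Absent | No | No | Neither |
| Ruled out | Present | No | Yes | Not related |

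Two of the four combinations have no category. The third row matters little: if timing rules the drug out, 'No' is the natural answer, and some other cause will nearly always be suspected. The second row carries the problem.

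**Step 2. Look for text that settles the second row.**

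- *Reasonable-possibility sentence (9.1.3).* It interprets the definition but does not remove the requirement that no other cause can be identified.
- *List of factors (9.1.3).* It tells the investigator to look for other diseases and drugs. It does not say how to code the event when one is found.
- *Protocol 9.1.1.* Its standard would make the event related unless the drug can be excluded. But 9.1.3 does not refer to it, and the 'Yes' text says the opposite.
- *SAP 7.13.1.* The strongest-relationship rule applies after each event has been coded, so it does not help.

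**Step 3. Follow the coding.** A literal reader of 'Yes' codes a second-row event not related; a literal reader of 'No' codes it related. Against the 9.1.1 standard, the first reader under-counts related events whenever the other cause does not fully explain the event. The recorded answer then goes into the drug-related TEAE and SAE rows, the TEAE table by relationship, and the reporting of SAEs after Day 90.

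**Step 4. Size.** The number of affected events depends on how often timing is plausible and another cause is present. Neither document gives that frequency, so no count or percentage can be derived. That two of four combinations are undefined needs no assumption.

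**The case against.** The best defence is that the definitions should be read with the rest of the section. Weighing alternative causes would be pointless if any identifiable cause barred 'Yes', so the factors and the reasonable-possibility sentence suggest an overall judgement, and 9.1.1 points the same way. Protocol 12.4 also requires eCRF completion procedures to be reviewed with investigators before enrolment, and those materials, which are not in the documents, may give guidance. This shows that investigators are not without direction. It does not remove the conflict, because 9.1.3 says relationship is to be assessed by the two definitions, and the 'Yes' definition contradicts the broader reading.

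The defence is stronger on consequences, and it rules out several inferences that a reader might draw:

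- *That gap events drop out of the tables as missing.* SAP 7.3.3 says "Other missing values will not be imputed and only observed values will be used", which might suggest this. But the answer is forced, so each such event carries a recorded value. The problem is inconsistent coding, and a rule for missing relationships would not address it.
- *That the related counts are wrong by some stated multiple.* Any such figure needs rates that the documents do not contain, and treating timing and other cause as independent would be implausible.
- *That one arm is favoured.* Causality is assessed blind, under the same text in both arms.
- *That SAEs during the study go unreported.* From randomization to the Day 90 visit, Protocol 9.3 requires all SAEs to be reported whatever their cause.
- *That expedited reporting follows the narrow 'Yes' definition.* Protocol 9.5 speaks of suspected adverse reactions, and 9.1.1 defines an adverse reaction by the broader standard. The documents do not show that the Sponsor is bound by the investigator's narrower answer.

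**Conclusion.** The wording defect is real, and its reach is limited. Under Protocol 9.1.3 an event with plausible timing and another possible cause meets neither definition of a compulsory yes/no scale, and the 'Yes' text conflicts with 9.1.1. Such events will be coded inconsistently or under-counted as related in the drug-related summaries of SAP 7.13.1 and in SAE reporting after Day 90. That they are common is a clinical inference from the population; their number cannot be computed from the documents.

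A reader might conclude that the safety comparison as a whole is unreliable. The documents do not support that. The all-causality tables, the SAE and discontinuation tables by system organ class and preferred term, the laboratory and vital-sign summaries and all efficacy analyses are independent of the causality answer. No test or decision rule in the documents uses it.

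**What to change.** Reword Protocol 9.1.3 to agree with 9.1.1:

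*Yes: there is a reasonable possibility that study drug caused or contributed to the event, i.e., the relationship cannot be ruled out, even if another cause is also possible. No: there is no reasonable possibility, because the timing or a fully explaining other cause rules it out.*

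In SAP 7.13.1, state that relationships recorded before the change used the unamended definitions and that safety interpretation rests on the all-causality tables by arm. SAP Section 3 allows such a change before unblinding.

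Asking sites to re-confirm only part of the events already recorded, such as SAEs or those soon after dosing, is not advised: the relationship table would then mix two standards by seriousness and onset day.

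The cost is a protocol amendment, which under Protocol 13.1 needs the same review and approval as the protocol itself, with communication to about 70 sites, and a short SAP addition. The broader standard will raise related counts in both arms. Events coded before and after the amendment will follow different definitions, which is why the SAP statement is needed.

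### The yes/no causality definitions in Protocol 9.1.3 leave some events with no valid answer and conflict with the adverse reaction definition in 9.1.1

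*Protocol*

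**What the plan says.** Protocol 9.1.3 has the investigator classify each adverse event for its potential relationship to study drug "using the categories of yes or no". Under Causality Assessment, both answers are defined by two conditions joined by *and*:

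- *No*: the time course "rules out a causal relationship and another cause (concomitant drugs, therapies, complications, etc.) is suspected".
- *Yes*: the time course "is consistent with a causal relationship and no other cause (concomitant drugs, therapies, complications, etc.) can be identified".

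The text then adds: "The definition implies a reasonable possibility of a causal relationship between the event and the study drug". A list of factors to consider follows (temporal sequence, other diseases, concomitant drugs, class effects, stress, pharmacology), with no rule for turning them into an answer.

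Protocol 9.1.1 sets the standard for an adverse drug reaction: a causal link "is at least a reasonable possibility, i.e., the relationship cannot be ruled out".

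The answer is used in three places. SAP 7.13.1 reports subjects with any drug-related TEAE and any drug-related SAE, and tabulates TEAEs by system organ class, preferred term and relationship. Protocol 9.3 requires every SAE from randomization to the Day 90 visit to be reported within 24 hours whatever its cause, but after Day 90 only those the investigator considers related. Protocol 9.5 has the sponsor expedite suspected unexpected serious adverse reactions.

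**The concern.** A two-category item needs definitions that cover every event, and its positive category should match the protocol's own concept of a reaction. Here neither holds. *Yes* fails as soon as another cause can be identified, whereas 9.1.1 asks only whether the drug can be excluded. The sentence about a reasonable possibility is offered as the meaning of the definition, but it is looser than the definition it explains.

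The uncovered case matters in this population. Subjects are mechanically ventilated, Protocol 1.3 permits concomitant antibiotics throughout, and the definition's own examples of alternative causes (other drugs, therapies, complications) are what intensive care supplies. An investigator facing such an event has to break one definition or the other, and different investigators may choose differently. If the *Yes* wording is taken literally, genuine suspected reactions go uncounted as related in a study whose primary objective includes safety and tolerability.

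**Working it through.** No sample size, power or error-rate figure bears on this point, and the plan gives no figure to reproduce. The check is logical: cross timing (compatible, or excluding the drug) with an alternative cause (present or absent), then apply the definitions as worded. An identified and a suspected alternative cause are treated as the same thing, which is a simplification.

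| Timing | Other cause | *Yes* in 9.1.3? | *No* in 9.1.3? | Adverse reaction under 9.1.1? |
|---|---|---|---|---|
| Compatible | Absent | Met | Not met | Yes, if not excluded |
| Compatible | Present | Not met: another cause is identifiable | Not met: timing does not exclude the drug | Yes, if not excluded |
| Excludes drug | Present | Not met | Met | No |
| Excludes drug | Absent | Not met | Not met: no other cause is suspected | No |

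Two of the four combinations have no valid answer.

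- **Compatible timing, other cause present.** This is the consequential gap. The event can be an adverse reaction under 9.1.1, yet it cannot be *Yes* under the wording of 9.1.3.
- **Timing excludes the drug, no other cause.** This second gap is minor. The event is not a reaction under 9.1.1, and *No* is plainly intended, but the joint condition blocks it.

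**Does other text close the first gap?** The reasonable-possibility sentence points towards *Yes* but contradicts the condition before it. The factor list tells the investigator to look for competing diseases and drugs without saying what to conclude when one is found. SAP 7.13.1 uses the two categories and gives no rule for the uncovered event. Protocol 9.2 mentions the view of either the investigator or the sponsor, but only on seriousness. The documents describe no separate sponsor causality assessment that would correct the coding.

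**Size.** Let q be the share of events that are reactions under 9.1.1 and also have another identifiable cause. Applied literally, the *Yes* definition admits at most 1 − q of those reactions. The documents give no value for q. As a pure assumption:

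- q = 0.5: at most 1 − 0.5 = 50% coded related.
- q = 0.9: at most 1 − 0.9 = 10% coded related.

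If every investigator instead followed the reasonable-possibility sentence, all of them could be coded related. Coding could fall anywhere between these limits and differ by site. The range illustrates the mechanism and is not an estimate.

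**The case against.** The best counter-argument accepts the gap and disputes its direction and reach.

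**Direction.** The uncovered event fails *No* as well as *Yes*, so the text does not push it into *No*. The request to judge potential relationship, the reasonable-possibility sentence and 9.1.1 all point a careful investigator to *Yes*. This stands in part. Under-classification is a risk, not a certainty, and inconsistent coding is the firmer claim. But the answer then depends on which of two conflicting sentences the investigator follows.

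**Safety reporting.** All SAEs to Day 90 are reported whatever their cause, so the investigator's answer controls SAE reporting only afterwards. This stands. On expedited reporting, the sponsor's duty in 9.5 concerns adverse reactions, which 9.1.1 defines broadly, and nothing says that only an investigator's *Yes* triggers it. That also stands. A reader might infer that fewer events will be expedited, but the documents do not say how the sponsor judges relatedness, so this is a possibility only.

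**The randomized comparison.** TEAEs by system organ class and preferred term, TEAEs by severity, SAEs and fatal SAEs are summarized by arm without using causality, and investigators code blinded. This stands. The main safety comparison is intact, and there is no reason to expect miscoding driven by knowledge of assignment. Blinding does not make the drug-related rows accurate, however.

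**Site guidance.** eCRF completion guidance may already cover the case. It is not among the documents, so this can be neither confirmed nor relied on.

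**Conclusion.** The causality definitions are wrong as written, rather than merely short of detail: they are not exhaustive, and the *Yes* test is stricter than the reaction standard in 9.1.1. Events with compatible timing and another identifiable cause are liable to be coded inconsistently and under-classified as related.

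The effect is confined to the drug-related TEAE and SAE rows and the by-relationship table in SAP 7.13.1, SAE reporting after Day 90, and possibly the identification of suspected reactions for expedited reporting. SAE reporting to Day 90, the all-TEAE comparisons by arm and the primary efficacy analysis are untouched.

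A reader might infer that the drug-related tables will be close to empty, or that the safety objective as a whole is compromised. The documents support neither. Some investigators can reasonably answer *Yes* under the looser sentence, the causality-free tables remain, and no document gives the share of events with a competing cause. The size therefore cannot be computed. The logical conclusion needs no assumption beyond reading the definitions literally; the practical importance rests on competing causes being common in ventilated ICU subjects, which is likely but not quantified.

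**What to change.** Reconcile Protocol 9.1.3 with 9.1.1 so that the two categories cover every event:

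- *Yes*: there is a reasonable possibility that study drug caused or contributed to the event (it cannot be ruled out), whether or not other causes exist.
- *No*: there is no reasonable possibility that it did.

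Keep the listed factors as guidance for reaching that judgement. This closes both gaps, and the table structure in SAP 7.13.1 can stay as it is.

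The cost is a wording change in the protocol, matching wording in any eCRF completion guidance, and a memo to sites. The downside is that somewhat more events will be coded as related, which is what 9.1.1 already implies. If events have already been coded when the wording changes, the study report should state which definition applied to them.
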